Shupyk National Medical Academy of Postgraduate Education, Kiev
Perinatal Prevention of AIDS Initiative, Odessa

United Kingdom / Ireland (CHIPS and CHIPS+ cohorts):

[name] (CHIPS and CHIPS+ overall PI) University College London, UK

Site PIs:

[name], [name] Great Ormond Street Hospital for Children NHS Foundation Trust, London (CHIPS)

[name], [name] Guy's and St Thomas' NHS Foundation Trust, London (CHIPS / CHIPS+)

[name] North Manchester General Hospital (Northern Care Alliance NHS Group), Manchester (CHIPS)

[name], [name] University Hospitals Birmingham NHS Foundation Trust, Birmingham (CHIPS, CHIPS+)

[name] Imperial College Healthcare NHS Trust, London (CHIPS / CHIPS+)
[name], [name] King's College Hospital NHS Foundation Trust, London (CHIPS, CHIPS+)

[name], [name] St George's University Hospitals NHS Foundation Trust, London (CHIPS, CHIPS+)

SUMMARY OF STUDY

SUMMARY INFORMATION TYPE	SUMMARY DETAILS
Acronym	EPPICC- SARS-CoV-2 antibody study
Long Title of Study	Prevalence of SARS-CoV-2 antibodies in children, adolescents and young adults living with HIV in Europe and South Africa
Version	3.0
Date	18 May 2021
MRC CTU at UCL ID	EPPICC SARS-CoV-2
REC #	17493/002
Study Design	Serial point prevalence survey
Setting	HIV clinics across Europe and South Africa.
Type of Participants to be Studied	Children and young adults living with HIV
Aim	To describe the prevalence and distribution of antibodies to SARS-CoV-2 in children and young adults living with HIV in Europe and South Africa
Sponsor	Penta Foundation
Number of Participants to be Studied	1150
Duration	18 months
Funder	Research grant from ViiV Healthcare. The MRC CTU at UCL is supported by the Medical Research Council programme grant MC_UU_12023/26. EPPICC is funded by grants from the Penta Foundation. CTAAC is funded by the National Institutes of Health, USA.
Chief Investigator	[name]

LAY SUMMARY

Scientific knowledge about the COVID-19 pandemic and the virus that is causing it (SARS-CoV-2) is developing rapidly, and we have a clearer idea of the population groups who are at higher risk of becoming infected, having serious illness, and dying. However, less is known about COVID-19 in children, adolescents and young adults living with HIV. It is not yet known whether, or how, HIV affects people's risk of being infected with the virus or becoming ill. This study aims to find out whether children and adolescents living with HIV have had the COVID-19 virus, even if they did not have symptoms and did not realise it at the time.

When a person is infected with a virus, their immune system fights the infection. As a result, they produce proteins called antibodies, and it may take a few weeks for enough antibodies to be made to be detected by a blood test. These antibodies may help protect the person from getting the same infection again. In this study, we want to find out how many children and adolescents living with HIV across Europe and South Africa have antibodies to the COVID-19 virus. We want to see if the proportion with antibodies is different in younger children compared to older adolescents and young adults, and whether it varies between different countries.

Some countries are rolling out vaccines against COVID-19 and have prioritised people living with HIV. We do not know if the immune response to vaccines in people living with HIV is similar to those without HIV, how long the antibodies last for and if it varies by age or any other characteristic.

Children and adolescents with HIV regularly attend hospital outpatient appointments, and during these appointments blood samples may be taken to monitor their health. In this study, we will invite these patients to be tested for antibodies to the COVID-19 virus during their routine visit. The participants will be asked a few short questions about COVID-19 diagnoses in their household and other risk factors for exposure to the virus, and if they have been offered and received any COVID-19 vaccine. We will collect information on their HIV, medications and any other illnesses they may have. At their next routine clinic visit, approximately 6 months later, we will test them again for antibodies. Testing twice will let us see how the percentage of children, adolescents and young adults with antibodies to the COVID-19 virus has changed over time. In South Africa, HIV-uninfected adolescents from a similar socioeconomic background to those living with HIV and recruited to the study will be invited to join this study, which will allow us to compare the prevalence of antibodies across the two groups.

The information from this study will help scientists and healthcare workers care for children, adolescents and young adults living with HIV during the ongoing COVID-19 epidemic in the best possible way. Participants may be given their test results, together with information about what the result means, depending on the usual practice within their clinic.

All of the data collected in this study will be stored securely at the MRC CTU at UCL, and will conform to the General Data Protection Regulation. The results of this study will be published on Penta's public website, presented at conferences and published in Open Access scientific journals.

A Steering Committee will provide guidance for the study, to make sure the research is relevant to people living with HIV and of high quality. Patients and the public will also be involved in the conduct of the research, as many HIV clinics involve their own patients in how the studies are run, and in making sure that results are circulated widely to interested groups.

CONTENTS

GENERAL INFORMATION.....	III
SUMMARY OF STUDY.....	VI
LAY SUMMARY	VII
CONTENTS	VIII
ABBREVIATIONS.....	X
1 BACKGROUND	1
1.1 MAIN AIM	2
1.2 OBJECTIVES.....	2
2 SELECTION OF PATIENTS	3
2.1 INCLUSION CRITERIA.....	3
2.2 EXCLUSION CRITERIA	3
2.3 INFORMED CONSENT	3
2.4 PARTICIPATING COHORTS	4
2.5 NUMBER OF PATIENTS	5
2.6 CO-ENROLMENT GUIDELINES	5

1 BACKGROUND

As of 14 October 2020, the WHO European region had reported over 7 million COVID-19 cases and almost 250,000 deaths [1]. At the time of initiating this study, although the number of reported cases has been lower in the African region (just over 1.2 million), likely due to both later arrival of the pandemic and incomplete reporting, over half of these have been in South Africa and over 18,000 COVID-19 deaths have been reported in the country [1].

Seroprevalence studies provide estimates of the percentage of the population that has either been infected with SARS-CoV-2 (the virus which causes COVID-19) or vaccinated against the virus, based on evidence of antibodies against the viral spike (S) or nucleocapsid (N) proteins. However, few published studies have included data from children and adolescents [2, 3]. The prevalence of antibodies to SARS-CoV-2 in children in (pre-vaccination) population studies has been estimated as ~3-4% in those aged 0-19 in Spain by mid-May 2020 [2], and 0.8% in 5-9 year-olds and 9.6% in 10-19 year-olds in Geneva by early May 2020 [3]. In England, seroprevalence in 1-24 year olds has been estimated as 5.2% (95% credible interval 3.2-7.8%) based on samples collected between May and August 2020 [4]. Whilst uncertainties remain about the extent and duration of protection that antibodies may provide, measuring seroprevalence is a first step towards understanding the proportion of a population that remains susceptible to infection and therefore the potential risk of future outbreaks.

There are currently limited and inconsistent data on the epidemiology of SARS-CoV-2 and COVID-19 in people living with HIV. The studies published to date have presented data on COVID-19 amongst adults living with HIV [5-11] but it remains unclear to what extent HIV affects the risk of infection, disease, severe disease or death. Some studies suggested that there may not an association between HIV and COVID-19 severity or mortality [5], whilst others suggest increased mortality amongst adults with COVID-19 co-infected with HIV compared to the HIV-uninfected population, even after adjustment for co-morbidities and other factors [11, 12]. These studies have not included children.

In some countries in Europe, there has been rapid scale up of COVID-19 vaccines and in the UK, persons living with HIV aged 16 years and above are included as one of the priority groups for vaccination [13]. There are very limited data on the uptake and immune response to vaccines in persons living with HIV and the duration of detectable antibodies.

Europe has some of the most well established cohorts of children born with HIV or who acquired HIV in early childhood, and many of these cohorts are part of the EPPICC (European Pregnancy and Paediatric Infections Cohort Collaboration) network, a collaborative network which combines data and expertise to answer questions about the health and care of children, adolescents and pregnant women living with HIV. EPPICC's activities include conducting the EPPICC Paediatric Study, a cohort study through which harmonised longitudinal clinical data are collected on children living with HIV. Data mergers, in which data from participating cohorts in geographically and epidemiologically diverse settings in Europe and Thailand are combined, take place approximately every 2-3 years. This allows follow-up of enrolled children to assess issues such as uptake, safety and effectiveness of novel ART drugs, and risk factors for outcomes such as clinical events and disengagement from care.

South Africa has a high prevalence of paediatric HIV, with differing epidemiology to that seen in Europe (e.g. children living with HIV in South Africa are, on average, younger than in Europe, and the prevalence of co-morbidities such as tuberculosis and malnutrition is higher in South Africa). The Cape Town Adolescent Antiretroviral Cohort (CTAAC) is a prospective cohort which follows adolescents who are infected with HIV, as well as HIV-uninfected adolescents of similar age, sex and socioeconomic background. Participants undergo a range of clinical and laboratory examinations every six months. Enrolment began at eight sites in Cape Town in 2013 and most participants are now aged 17-20 years.

Both Europe and South Africa have been heavily affected by the COVID-19 pandemic, and together these settings provide an opportunity to assess the seroprevalence of antibodies to SARS-CoV-2 in children living with HIV in settings differing in HIV epidemiology, healthcare provision and response to COVID-19 (e.g. the prevalence of risk factors for disease and the extent and duration of mitigation measures such as “lockdown”). The cohorts within EPPICC and South Africa provide a sampling frame from which to select children and adolescents living with HIV to estimate seroprevalence.

1.1 MAIN AIM

The overall aim of this study is to describe the prevalence and distribution of antibodies to SARS-CoV-2 in children and adolescents living with HIV in Europe and South Africa.

1.2 OBJECTIVES

Primary objective:

- To estimate prevalence of SARS-CoV-2 antibodies in the paediatric and adolescent HIV population and how this changes over time, overall and by key age groups and regions

Secondary objectives:

- To assess factors associated with presence of SARS-CoV-2 antibodies (including demographic factors, antiretroviral treatment, HIV-associated factors or co-morbidities and exposure to household members with COVID-19, receipt of COVID-19 vaccine)
- To estimate the incidence of changes in antibody status to SARS-CoV-2 and associated factors

2 SELECTION OF PATIENTS

2.1 INCLUSION CRITERIA

All children and adolescents attending routine HIV clinic visits will be invited to join the study if they meet all of the inclusion criteria below:

- < 18 years at HIV diagnosis
- Current age under 25 years
- Attending routine HIV care in a participating clinic
- Currently in follow-up in either CTAAC, CHIPS+ or a cohort which contributes to EPPICC
- If aged ≥ 16 years (or local legal adult age), willing and able to give informed consent to participate in the study
- If aged <16 years (or local legal adult age), a parent/carer able to give informed consent for participating in the study (and, depending on local requirements, those aged ≥ 10 years, with capacity, to also provide assent).

In addition, in South Africa HIV-uninfected adolescents will be eligible to participate in the study during planned study visits if they meet the following inclusion criteria:

- Current age under 25 years
- In follow-up in the CTAAC study
- If aged ≥ 18 years, willing and able to give informed consent to participate in the study
- If aged <18 years, a parent/carer is able to give informed consent for participating in the study and participant willing and able to provide assent.

2.2 EXCLUSION CRITERIA

Children and adolescents are ineligible if they:

- Are taking part in a COVID-19 / SARS-CoV-2 vaccine study at enrolment

However, should a participant who is enrolled in the EPPICC-SARS-CoV-2 study subsequently join a COVID-19 / SARS-CoV-2 vaccine study or receive a COVID-19 / SARS-CoV-2 vaccine, these are not reasons for exclusion from this study. Data will be collected on vaccine receipt and participation in vaccine studies.

At the time of writing this protocol, COVID-19 / SARS-CoV-2 vaccines are being made available at different speeds across the participating countries, so there is a possibility that study participants may receive a vaccine over the course of this study. Participation in this study must not influence or delay the choice to receive a COVID-19 vaccination, either through participation in a trial or through a vaccination programme.

2.3 INFORMED CONSENT

Participants and, where necessary, their parents / carers will be asked for informed consent before taking part in the study.

Children / adolescents and their parents / carers (as appropriate) will receive a Participant Information Sheet detailing study procedures, together with a Consent Form. To participate in the study, participants will need to:

- Agree to give a blood sample at up to two different time points, for testing for SARS-CoV-2 antibody. Participants who have previously received an antibody test as part of standard care or a research study in their clinic at least 4 months ago will be offered one additional test.
- Agree for the site investigator to determine whether the local laboratory has any stored blood samples for the participant (taken on or after 1 March 2020) and for any such samples to be tested for SARS-CoV-2 antibody
- Complete a short questionnaire at up to two different time points
- Agree to the research team collecting clinical data including on their HIV if applicable (e.g. treatment status, CD4 counts and viral loads)
- Agree to record linkage to data collected in ongoing studies in which they may be participating (e.g. EPPICC, local or national HIV cohort studies and / or local or national COVID-19 studies).

Consent may be given in person or, if clinics are operating remotely, consent may be provided via phone or video call if permitted under local guidelines and approvals.

Participants may withdraw from the study at any time without giving a reason.

Patients not consenting to participate will continue to receive their usual care in routine follow-up at the clinic. If a patient chooses not to participate in the study or subsequently withdraws, there will be no impact on their clinical care.

2.5 NUMBER OF PATIENTS

A total of 1150 participants will be included. This comprises 650 participants to be enrolled from the EPPICC cohorts in Europe and 500 from the South African CTAAC cohort, which will include ~50-100 HIV uninfected participants as a comparator group. The sample size calculation is described in Section 6.1.

2.6 CO-ENROLMENT GUIDELINES

Participants should not be enrolled in this study if they are already enrolled in a SARS-CoV-2 vaccine trial at time of entry to the study. However participants included in this study may be co-enrolled in clinical trials and other studies at the discretion of the treating clinician.

Enrolment in SARS-CoV-2 vaccine studies **after** enrolment in this study is permitted and must not be influenced by participation in this study.

3 STUDY PROCEDURES

3.1 STUDY DESIGN

This is a serial point prevalence survey of representative samples of children and adolescents attending routine HIV care in the participating clinics and cohorts, with repeat antibody testing at baseline (study entry) and approximately 6 months after study entry (Table 1), and in some clinics further long-term follow-up through linkage to data collected in an ongoing longitudinal cohort study. In South Africa approximately 50-100 HIV-uninfected adolescents enrolled in the ongoing CTAAC cohort will be invited to participate in this study as a comparator group.

Eligible participants who are interested in joining the study will be asked for their consent to participate if aged ≥ 16 years or as per local legal requirements. For participants aged <16 years, consent of their parent/carer will be sought as per legal requirements. Assent will be sought from children and adolescents aged 10 years and older, depending on local ethics requirements. Potential participants and their parents / carers should be allowed at least 5-10 minutes to consider whether or not to take part; where possible, it may be helpful to give patients copies of the participant information sheet while they wait for their appointment.

Data collection will be conducted at HIV clinics during routine visits in clinical care (in the European cohorts) or planned study visits (in CTAAC, for both CLWHIV and HIV-uninfected adolescents), and no additional study visits will be required.

At entry to the study the participant will give a venous blood sample for a SARS-CoV-2 antibody test (the exact test used will depend on local clinical practice). An additional serum sample will be taken at the same time as a routine blood draw and leftover sample will be used if possible. At the next scheduled routine HIV clinic/study visit approximately 6 (no less than 3 and up to 13) months later, a repeat venous blood sample will be collected for a second antibody test. At each visit, participants (or their parents/carers) will be given a COVID-19 questionnaire, asking short questions about any COVID-19 diagnoses in themselves or among household members and other possible exposures to the virus. All study procedures will be carried out following local COVID-19 guidelines.

If participants have previously (after 1 March 2020 and at least four months before the date of the first sample collected as part of this study) had a blood sample tested for SARS-CoV-2 antibody as part of their routine HIV care or another research study (for which the result is available in their medical records), that test will be considered as the first test for this study. These participants would therefore provide an additional blood sample at only one study visit. Clinical data corresponding to the time of the first sample collection will be extracted.

If participants have previously (after 1 March 2020 and at least four months before the date of the first sample collected as part of this study) had blood taken for other reasons that is still stored, this may also be tested for SARS-CoV-2 antibodies. In these cases, this would be considered the first test for this study and these participants would provide an additional blood sample at only one study visit. Clinical data corresponding to the time of the first sample collection will be extracted.

Participants who are followed in cohorts which are part of the EPPICC network will continue to be followed up through the ongoing EPPICC Paediatric Study.

Table 1: Study participant timeline

	Baseline	2nd visit at 6 months*
Eligibility screen	X	
Informed consent	X	
Blood sample for SARS-CoV-2 antibody	X	X
COVID-19 patient questionnaire	X	X
Clinical data collection	X	X

* Participants who have results available from a previous blood test for SARS-CoV-2 antibody in the previous 4 months (as part of routine care or research) do not require a second test.

Participants will be given the result of their SARS-CoV-2 antibody tests with guidance on how to interpret the results, unless this conflicts with the clinic or study's usual practice.

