3.2 ENROLMENT AND FOLLOW-UP

We aim to start enrolment from November 2020 (pending ethics approval) and enrol participants for approximately twelve months or until the sample size is met. The enrolment period may be extended in the event of disruptions to clinic services due to COVID-19. Where feasible, all children and adolescents meeting the inclusion criteria and attending the participating clinics during this period will be invited to take part; where this is not possible, a convenience sample of children and adolescents (e.g. those attending clinic on a specified day of the week) should be invited. The invitation to participate should be independent of the patient's probability of having been exposed to COVID-19.

Participants will be considered lost to follow-up for the purposes of this study if they have not provided the second blood sample by 13 months after the enrolment date.

Participants enrolled in the EPPICC Paediatric Study or CTAAC will continue to be followed up as part of the ongoing study.

Logs will be kept of the number of children and adolescents declining the invitation to participate, with reasons for refusal where available.

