6.2 ANALYSIS PLAN

Data will initially undergo extensive logic and consistency checks and any potential errors will be resolved through discussion with cohort/clinic data managers.

Proportions with SARS-CoV-2 antibody at baseline and follow-up and the number/incidence of changes in antibody status between baseline and subsequent test will be estimated overall and by key patient characteristics, region, history of symptomatic COVID-19, contact with COVID-19 cases, receipt of COVID-19 vaccine. Factors associated with the presence of SARS-CoV-2 antibody, changes in

antibody status and any subsequent COVID-19 diagnosis (if numbers allow), will be explored using univariable and multivariable logistic and Poisson regression. Exposures of interest include age, sex, ART class and regimen (e.g. protease inhibitor- or tenofovir-based versus other), CD4 count, viral load, ethnicity, BMI-for-age z-score, co-infections (e.g. tuberculosis), co-morbidities, receipt of/duration since COVID-19 vaccine and household size.

The association between HIV status and SARS-CoV-2 seropositivity, changes in antibody status and subsequent COVID-19 diagnosis will be assessed in the South African cohort (which includes HIV-uninfected children as well as CLWHIV) using similar methods. Directed acyclic graphs may be used to determine which covariates to include in the models and to aid interpretation of the results.

If there is substantial variation in the type of antibody test used (anti-S versus anti-N), analyses will be stratified by type of test. For participants with positive results at both baseline and follow-up and if data allow, quantitative antibody results will be explored to qualitatively describe the possible contribution of re-exposure boosting antibody responses (versus persistence of an existing response).

In sensitivity analyses, we will investigate the implications of misclassification of results due to imperfect sensitivity / specificity of the serological tests used.

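### The plan calls its samples representative, but the pooled and European prevalences would reflect whichever mix of cohorts enrols, with no standardised figure or comparison with the eligible population

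*Combined protocol and SAP*

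**What the plan says.** The primary objective (Section 1.2) is antibody prevalence in the paediatric and adolescent HIV population and its change over time, overall and by key age groups and regions.

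- **Claim about the sample (Section 3.1).** "This is a serial point prevalence survey of representative samples of children and adolescents attending routine HIV care".
- **Frame (Section 1).** The cohorts "provide a sampling frame from which to select children and adolescents living with HIV to estimate seroprevalence".
- **Selection (Section 3.2).** The default is broad: "Where feasible, all children and adolescents meeting the inclusion criteria and attending the participating clinics during this period will be invited to take part". The fallback is "where this is not possible, a convenience sample of children and adolescents (e.g. those attending clinic on a specified day of the week) should be" approached. There is a safeguard: "The invitation to participate should be independent of the patient's probability of having been exposed to COVID-19". Refusals are logged as numbers, with reasons where available.
- **Stopping (Section 3.2).** Sites "enrol participants for approximately twelve months or until the sample size is met".
- **Numbers (Sections 2.5 and 6.1).** 650 from Europe and 500 from South Africa, the latter including about 50-100 HIV-uninfected. Table 3 lists 1093 eligible in Europe and 400 eligible participants living with HIV in South Africa.
- **Estimator (Section 6.2).** "Proportions with SARS-CoV-2 antibody at baseline and follow-up" are estimated overall and by patient characteristics, region and other factors. The only bias analysis named concerns test misclassification.

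**The concern.** A sample is representative through its selection or through adjustment in the analysis. Here the selection rule varies by site, the European total can be filled by any mix of cohorts, and no adjustment is named. The pooled and European figures are then averages weighted by enrolment. The primary objective is about the eligible population, whose composition is known at least by cohort.

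This would be harmless if prevalence were the same everywhere, but the plan expects otherwise. It sets out to compare ages and countries, cites 0.8% at 5-9 years against 9.6% at 10-19 years (Section 1), and notes that vaccines are arriving at different speeds in different countries (Section 2.2). At stake is the headline prevalence: its confidence interval covers sampling error only, not error from the cohort mix.

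**Working it through.** **1. The plan's own precision (Section 6.1).** Half-width = 1.96 × √(p(1−p)/n) with p = 0.10.
- n = 650: 2.31 points (stated as 2).
- n = 500: 2.63 points; n = 400: 2.94 points (stated as 3).

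The figures reproduce to the whole point. They assume simple random sampling.

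**2. Is there room for the European mix to shift?** 650/1093 = 59.5%. At the plan's 70% participation, 0.70 × 1093 = 765 would join, about 115 more than the places. The cap therefore binds if participation exceeds 59.5%.

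**3. Europe, UK against the rest.** The UK is 442/1093 = 40.4% of the frame. Cap each cohort at 70%:
- Largest UK share: 0.70 × 442 = 309.4; 309.4/650 = 47.6%.
- Smallest UK share: 650 − 0.70 × 651 = 194.3; 194.3/650 = 29.9%.

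Error in the crude figure = (sample share − frame share) × prevalence difference. The differences are assumptions.

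| UK minus rest | Range of error (points) |
|---|---|
| 5 points | −0.5 to +0.4 |
| 10 points | −1.1 to +0.7 |
| 20 points | −2.1 to +1.4 |

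**4. Europe and South Africa pooled, participants living with HIV.** Taking 400 from South Africa, its share of the target sample is 400/1050 = 38.1%; its share of the frame is 400/1493 = 26.8%. This imbalance is built into the targets. The prevalences are assumptions.

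| Europe / South Africa | Crude | Standardised |
|---|---|---|
| 5% / 10% | 6.9% | 6.3% |
| 5% / 20% | 10.7% | 9.0% |
| 10% / 30% | 17.6% | 15.4% |

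For the last row: 0.619 × 10 + 0.381 × 30 = 17.6, and 0.732 × 10 + 0.268 × 30 = 15.4.

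**5. Age mix.** With the cited 0.8% and 9.6%, a 10-point error in the age split moves the crude figure by 0.10 × 8.8 = 0.88 points.

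**6. What standardising costs in precision.**
- *Europe/South Africa weights.* European participants get weight 1093/650 = 1.68 and South African participants 1. The Kish design effect n·Σw²/(Σw)² is 1.054. At p = 0.10 the half-width goes from 1.81 to 1.86 points.
- *An unfavourable case.* Ukraine enrols 34 of 170 and the other cohorts 616 of 923 (66.7%, within the 70%). Assume 25% prevalence in Ukraine and 8% elsewhere. Frame value: (170 × 0.25 + 923 × 0.08)/1093 = 10.6%. Crude: (34 × 0.25 + 616 × 0.08)/650 = 8.9%, an error of −1.75 points. Standardised variance: (170/1093)² × 0.25 × 0.75/34 + (923/1093)² × 0.08 × 0.92/616 = 0.000219 (standard error 1.48 points). Crude variance: 0.0889 × 0.9111/650 = 0.000125 (1.12 points). The ratio is about 1.75. Including its bias, the crude figure's root mean square error is √(1.12² + 1.75²) = 2.08 points, against 1.48 standardised.

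**The case against.** Much of the opposing case stands.

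- Inviting everyone is the default and convenience sampling only the fallback. The rule that invitation must not depend on likely exposure addresses the most damaging selection. It does not govern the cohort mix, attendance frequency or refusal.
- The absence of cohort targets cannot be proved. Section 2.4 on participating cohorts is not in the text available; the statement covers only what is visible.
- Section 6.2 never says that the overall proportion is unweighted; this is inferred because no weighting is named.
- Age and region rows are planned and would reveal differences in prevalence. A reader might infer that no planned analysis would show the problem, which goes too far. The rows do not repair the pooled figure or selection within a row.
- A reader might also infer that the estimates simply follow the fastest-recruiting clinics. That is conditional: below 59.5% European participation the cap never binds, although unequal participation can still shift the mix. In South Africa the target is close to the whole eligible cohort.
- Frame data are imperfect. Table 3 is provisional, EPPICC mergers occur every 2-3 years, Section 2.1 names CHIPS+ separately from contributing cohorts, and non-EPPICC sites submit data for the study visits only. Greece has 22 eligible, so fine cells would be sparse.

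These points argue against making a finely standardised figure primary. They do not argue against placing a cohort-standardised one beside the crude one.

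**Conclusion.** The concern holds in a limited form. The description in Section 3.1 is stronger than Section 3.2 supports, and Section 6.2 names nothing to bring the pooled or European figure back to the eligible population.

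The likely size is modest and rests on assumed prevalences: up to about 1.1 points in Europe for a 10-point UK-versus-rest gap, 2.1 for a 20-point gap, and 2.3 (17.6% against 15.4%, before rounding) in the pooled figure at 10% versus 30%.

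A reader might conclude that the error will exceed the quoted precision of ±2%. The documents do not establish this. An error of 3.1 points (11.6% crude against 14.7%) arises if Ukraine enrols 34 and prevalence is 40% there against 10% elsewhere, but no figure in the plan supports a 30-point gap. In the opposite direction, Ukraine at the 70% cap (119 enrolled) gives 15.5% against 14.7%, only 0.8 points. The cited general-population figures for Spain (about 3-4%) and England (5.2%) are close, and the UK and Spanish cohorts make up 742/1093 = 68% of the European frame. Those figures are pre-vaccination, so later gaps could be wider.

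**What to change.** This is a cheap improvement, made by changes of wording and a small added analysis.

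1. In Section 6.2, beside each crude overall and European prevalence in participants living with HIV, report a figure standardised to the final eligible counts by cohort (Table 3, updated). Add broad age groups only where frame data exist and cells are not sparse.
2. Tabulate participants against eligible cohort members on age and sex, and on last CD4 count and viral load where held.
3. In Section 3.1, replace the claim of representative samples with the sampling actually used.

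No extra participants, blood or visits are needed. The cost is wider intervals for the standardised figure: a design effect of about 1.05 for the Europe/South Africa weights, and variance up to about 1.75 times if a high-prevalence cohort such as Ukraine enrols only 34. Standardising does not correct over-selection of frequent attenders or other unmeasured selection, and the report should say so.
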